6.2 Design

Phase III studies are usually randomized, often with one group receiving the current standard treatment. These studies may or may not be placebo-controlled. However, the population with co-infection with HCV and HIV is difficult to treat and has very few treatment options. In this population, the use of a standard care group is difficult to justify ethically because response rates with such a regimen are low and because the toxicity of the current standard of care (i.e., PEGIFN + RBV) is considerable.

In this regard, we could establish that SVR in the historical control group is between the 10% (95% confidence interval [CI]: 5%-18%) in previously treated patients and 26% described in the placebo control group in the phase II study of HCV-infected patients not previously treated with boceprevir

STUDY PROCEDURES

Selection Evaluations	
Clinical Evaluations	Selection
Informed consent	X
Inclusion and exclusion criteria	X
Assignment of the selection number	X
Vital signs	X
Weight Determination	X
Height determination	X
Demographics	X
Medical history	X
Physical examination	X
Adverse events	X
Concomitant medications	X
Liver biopsy or Fibroscan (not necessary if performed prior to 18 months)	X
Ultrasound (in patients with bridge fibrosis or cirrhosis) (6 months prior)	X
Confirmation of the use of contraceptive methods by the patient and his or her partner	X

Treatment Visit Schedule														
Clinical Evaluations	Day 1	ST 2	ST 4	ST 6	ST 8	ST 10	ST 12	ST 16	ST 20	ST 24	ST 30	ST 36	ST 42	ST 48/dFT
Inclusion and exclusion criteria	X													
Vital signs	X	X	X	X	X	X	X	X	X	X	X	X	X	X
Weight	X									X				X
Physical examination	X		X				X			X		X		X
Adverse events	X	X	X	X	X	X	X	X	X	X	X	X	X	X
Concomitant medications	X	X	X	X	X	X	X	X	X	X	X	X	X	X
Confirmation of the use of contraceptive methods by the patient and his or her partner	X	X	X	X	X	X	X	X	X	X	X	X	X	X
Simplified Compliance Questionnaire	X	X	X		X		X		X	X		X	X	X
Haematology	X	X	X	X	X	X	X	X	X	X	X	X	X	X

TP/TPP	X					X			X				X
Blood biochemistry (simplified, fasting)		X	X		X		X		X		X		
Blood biochemistry (complete, without fasting)	X			X			X		X		X		X
Thyrotropin (TSH)	X					X			X		X		X
Serum pregnancy test (women only)		X											X
Test of pregnancy in urine (in women only)		X	X	X	X	X	X	X	X	X	X	X	X
Samples for pharmacogenetics	X												
HCV RNA CPR*	X		X		X		X		X				X

All laboratory specimens should be obtained prior to administration of the first dose of study medication.

* Samples will be obtained for genotypic resistance testing if the patient has >100 IU/mL at week 12 or later.

Complete blood biochemistry: ALT, AST, creatinine, alkaline phosphatase, gammaglutamyltransferase (GGT), total bilirubin (direct and indirect), total proteins, albumin, uric acid, urea nitrogen, glucose, HbA1C (in patients diagnosed with diabetes, whether they are receiving pharmacological treatment or controlled with diet), amylase, lipase, sodium, potassium, chloride, phosphorus, calcium, triglycerides, and cholesterol.

Simplified blood biochemistry: alanine aminotransferase (ALT), aspartate aminotransferase (AST), creatinine, alkaline phosphatase, total bilirubin (direct and indirect), urea nitrogen, total proteins, albumin, uric acid and glucose.

Fibrosis evaluation: This will be done by liver biopsy or Fibroscan. In patients without cirrhosis on histology or Fibroscan, evaluation must have been performed no more than 18 months prior. A result of 12 kilopascals or more on the Fibroscan test would allow the patient to be considered cirrhotic.

Ultrasound: Patients with bridge fibrosis or cirrhosis must have an ultrasound performed within 6 months prior to inclusion in the study.

6.3 Guidelines for BOC Dose Modification

The dose of BOC cannot be reduced in the study.

Grade 1 and 2 AEs require close follow-up but no change in treatment.

All grade 3 toxicities will be treated by the facility investigator as appropriate. Any grade 4 toxicity that, in the opinion of the centre's investigator, is directly related to BOC, will be treated with the permanent suspension of the latter.

In case of intolerance to the BOC, its administration will be suspended; The dose cannot be reduced. If BOC is temporarily or permanently stopped, patients may continue to receive PEG-IFN and RVB.

6.4 Trial treatments

DRUG SUPPLY AND LABELLING

In this study, 2 drugs already on the market and authorized for use in HIV-HCV co-infected patients will be used; peginterferon and ribavirin; The study drug, boceprevir, will be provided by MSD throughout the study and distributed by the Coordinating Center. For clinical trials carried out in Spain, relabelling in Spanish is mandatory.

See section 4.3

6.5 Duration of the trial

The approximate expected duration for the inclusion of patients is 2 months, and the duration of treatment and follow-up of the included patients will be extended by a maximum of 72 weeks

6.6 Termination and/or Discontinuation Criteria

The treatment will be **compulsorily** terminated during the study for any of the following reasons:

- Patient with HCV RNA >100 IU/mL in ST12 or detectable HCV RNA in ST24.
- Suicide or homicide thoughts or attempts.
- Severe depression or major depressive episode.
- Positive test result for non-prescription opioids, methamphetamines, or cocaine.
- Pregnancy during the study.
- Virological rebound, defined as:

Any patient who obtains an undetectable HCV RNA and subsequently presents an HCV RNA > 1,000 IU/ml.

Once virologic rebound has been identified, genotypic resistance will be characterized by HCV RNA sequencing in suitable samples, such as those collected at the time of rebound and during the follow-up period.

Treatment **may** be terminated during the study for any of the following reasons:

- The medical investigator determines that a SAE is possibly or likely related to the study drug.
- Failure to administer, evaluate, or other study requirements.

6.7 End of test

The end of the trial will be considered the time of the last visit of the last subject recruited.

7. Subject Selection

7.1 Criteria for inclusion of subjects

A patient must meet ALL of the criteria listed below in order to participate:

1. To participate in the study, patients must have been treated with peginterferon alfa-2a plus ribavirin or peginterferon alfa-2b plus ribavirin for a minimum of 12 weeks. If a patient has received more than one of these guidelines, the most recent one will be considered.
2. The patient must have a previously documented HCC caused by genotype 1 virus (subtype a or b). Patients with other genotypes or with mixed genotypes will not be able to participate. The HCV RNA result at the screening visit should confirm genotype 1 virus infection and be >10,000 IU/mL.
3. The patient must have a liver biopsy with HCC-compatible histology and no other etiology or evaluation with Fibroscan. In the event of:
 - a. **Absence of cirrhosis.** Biopsies or Fibroscan must have been done within 18 months prior to the screening visit.
 - b. **Cirrhosis** No specific time frame is required.
4. All patients with cirrhosis should have an ultrasound scan performed within 6 months prior to the screening visit.
5. Patients must be receiving stable antiretroviral therapy with a CD4 lymphocyte count greater than 100/mm³ and an undetectable HIV plasma viral load (< 50 copies/mL) for more than 6 months. Antiretroviral therapy should contain raltegravir (at least for the past 6 weeks).
6. The patient must be 18 years of age or older.
7. HIV treatment should not contain EFV, NVP, ddI, d4T, AZT, or HIV protease inhibitors.
8. The patient should weigh between 40 and 125 kg.
9. The patient and partner must commit to acceptable contraception from at least 2 weeks prior to Day 1 and until at least 6 months after the last dose of study drug. (negative pregnancy test in women of childbearing potential) (Postmenopause is defined as the absence of menstruation during the year prior to study entry.)
10. Patients must be willing to give written informed consent and, in the opinion of the investigator, be able to follow the protocol visit design.

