4.3 Treatment Regimen

PEG-IFN alfa-2a or 2b and ribavirin will be provided by each hospital and will be administered in accordance with the approved technical data sheets.

BOC (Boceprevir). Provided by the study sponsor.

Description:

BOC is supplied in 200 mg capsules. Each capsule contains 200 mg of BOC, sodium lauryl sulfate, microcrystalline cellulose, lactose monohydrate, croscarmellose sodium, pregelatinized starch, and magnesium stearate packaged in number 0 hard gelatin capsules. Each capsule contains approximately 56 mg of lactose monohydrate. In people with lactase deficiency, the clinical manifestations of lactose intolerance require 3 to 5 g of lactose (4 to 7 times the total amount of BOC capsules) to appear.

Route of administration: oral

Dosage: total daily 2400 mg, (12 capsules).

Storage: keep in the fridge at a temperature between 2°C and 8°C. The products of the study must be stored in a safe place with limited access and in the storage conditions specified on the supply label.

[figure not shown]
Dosage Schedule:

Boceprevir is administered three times a day using a dosing schedule of 4 capsules every 8 hours. Actual times of dose administration may be modified to fit the patient's schedule, although 7- to 9-hour

intervals between administrations should be maintained. All doses of boceprevir will be given with food (a small snack is sufficient).

Study period and treatment:

All patients will receive an initial 4 weeks of bitherapy with Peg-Interferon and ribavirin (PR).
-If there is a decrease in HCV RNA greater than 1 logarithm with respect to baseline HCV-RNA, the patient will be included in the treatment scheme detailed below.

-If the RNA drop is ≤ 1 log at week 4, PR/boceprevir will be administered for an additional 44 weeks. All cirrhotic patients will receive PR for 4 weeks, followed by RP/boceprevir for another 44 weeks

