7.2 Criteria for exclusion of subjects

Patients who meet ANY of the following criteria will be excluded from the study:

1. Patients with confirmed hepatitis B virus co-infection (HBsAg positivity).
2. Patients with chronic HCV infection of genotypes other than 1
3. CD4 lymphocyte count <100 cells/mm³.
4. HIV RNA in plasma greater than 50 copies/mL
5. Platelet count less than 80,000/mm³

6. Patients who had to discontinue prior interferon or ribavirin therapy due to a serious adverse event that the investigator considered possible or probably related to ribavirin or interferon.
7. Treatment with ribavirin in the previous 90 days and with any interferon alfa in the month prior to the screening visit.
8. Hepatitis C treatment with any investigational product. Previous treatments with phytotherapy products with known hepatotoxicity are grounds for exclusion.
9. Participation in another clinical trial within 30 days prior to randomization or intention to participate in another clinical trial during participation in the present study.
10. History of hemoglobinopathy (e.g., thalassemia) or other cause of hemolysis, or hemolytic tendency.
11. Signs of decompensated liver disease, such as a history or presence of clinical ascites, hemorrhagic varicose veins, or hepatic encephalopathy.
12. Diabetic or hypertensive patients with signs of clinical importance on ophthalmological examination.
13. Pre-existing, unstable, or untreated psychiatric illness.
14. Any known pre-existing medical conditions that could interfere with the patient's participation in the trial and its completion.
15. Any current signs of alcoholism or other drug use.
16. Patients receiving opioid agonist substitution therapy but not participating in any opioid substitution maintenance program.

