- Dose delay of 3 to 5 days: Giving subsequent doses every 5 to 6 days until the patient gets back to their original schedule (for example, if Monday is the usual day of administration and the dose is delayed until Saturday, the next dose will be given on Thursday, the next dose on Tuesday, and the next dose on Monday).
- 6-day dose delay: discontinue that week's dose and continue with the usual schedule the following week (e.g. if Monday is the usual day of administration but the dose is delayed until the following Sunday, the dose is considered to have been interrupted and the next injection will coincide with the following week's dose, on Monday).
- Dose delay of 7 or more days: The investigator may resume administration of the study drug at any time up to 28 days after the last dose and, if necessary, administer the dose every 5 or 6 days until the weekly dose is received on the patient's usual scheduled day.

Treating the Side Effects of RBV

The most common AA in RBV treatment is anemia, which may be due to hemolysis or decreased release of red blood cells from the bone marrow. Anemia usually appears 1 to 2 weeks after you start receiving RBV and usually goes away within 4 to 8 weeks of withdrawal or reduction of the drug's dose. In patients with anemia secondary to RBV-induced hemolysis, an elevation of indirect bilirubin is common. BOC may increase the incidence or severity of anemia. In case of anaemia during treatment with BOC and RBV, the dose adjustment of RBV, as described below, takes precedence over BOC.

NOTE: A serious side effect of RBV is its teratogenicity; therefore, it is recommended not to administer RBV to pregnant or breastfeeding women and to men whose partner is pregnant. Women who become pregnant during the study will be required to discontinue study treatment and undergo withdrawal assessments.

The dose of RBV in this study will depend on weight at study entry (see section 5). The following table shows the recommendations for dose reduction in case of anemia. The administration of epoetin (EPO) will be at the discretion of the centre's researcher. If the administration of RBV is temporarily or permanently stopped, patients may continue to receive PEG-IFN and BOC.

Board. Recommended RBV dose reduction in anaemia

	Starting dose	Measure
--	---------------	---------

Hemoglobin <10 g/dL, ≥8.0 g/dL.	1,400 mg/day 1,200 mg/day	Decrease RBV to 1,000 mg/day
	1,000 mg/day	Decrease RBV to 800 mg/day

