Prior to the start of treatment, a clinical examination, electrocardiogram and blood and urine sample will be taken (*SEE TABLE OF DAILY DETERMINATIONS*).

The data will be collected through an online electronic CRD.

15. Financing and Insurance

The promoter has taken out civil liability insurance in accordance with current regulations.

16. Publication Policy

The Promoter undertakes to publish the results, both positive and negative, of this study as stated in art. 39 of RD 223/2004.

17. Table of examinations and treatment during follow-up

Treatment Visit Schedule														
Clinical Evaluations	Day 1	ST 2a	ST 4	ST 6	ST 8	ST 10	ST 12	ST 16	ST 20	ST 24	ST 30	ST 36	ST 42	ST 48/dFT
Inclusion and exclusion criteria	X													
Vital signs	X	X	X	X	X	X	X	X	X	X	X	X	X	X
Weight	X									X				X
Physical examination	X		X				X			X		X		X
Adverse events	X	X	X	X	X	X	X	X	X	X	X	X	X	X
Concomitant medications	X	X	X	X	X	X	X	X	X	X	X	X	X	X
Confirmation of the use of contraceptive methods by the patient and his or her partner	X	X	X	X	X	X	X	X	X	X	X	X	X	X
Simplified Compliance Questionnaire	X	X	X		X		X		X	X		X	X	X
Haematology	X	X	X	X	X	X	X	X	X	X	X	X	X	X
TP/TTP	X						X			X				X
Blood biochemistry (simplified, fasting)		X	X		X		X		X		X		X	
Blood biochemistry (complete, not fasting)	X			X				X		X		X		X
Thyrotropin (TSH)	X						X			X		X		X
Serum pregnancy test (women only)	X													X
Urine pregnancy test (women only)		X	X	X	X	X	X	X	X	X	X	X	X	X
Samples for pharmacogenetics	X													
HCV RNA CPR*	X		X		X		X			X				X

All laboratory specimens should be obtained prior to administration of the first dose of study medication.

- Samples will be obtained for a genotypic resistance test if the patient has >100 IU/mL at week 12 or later. A single blood sample will be obtained for genetic studies.

Complete blood biochemistry: ALT, AST, creatinine, alkaline phosphatase, gammaglutamyl transferase (GGT), total bilirubin (direct and indirect), total proteins, albumin, uric acid, urea nitrogen, glucose, HbA1C (patients diagnosed with diabetes, either receiving pharmacological treatment or controlled with diet), amylase, lipase, sodium, potassium, chloride, phosphorus, calcium, triglycerides, and cholesterol.

Simplified blood biochemistry: alanine aminotransferase (ALT), aspartate aminotransferase (AST), creatinine, alkaline phosphatase, total bilirubin (direct and indirect), urea nitrogen, total proteins, albumin, uric acid and glucose.

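### Section 7 screens for pregnancy but does not exclude breastfeeding women or men whose partner is already pregnant, two groups for whom section 10.3 advises against ribavirin

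*Combined protocol and SAP*

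**What the plan says.** Criterion 9 in section 7.1 requires the patient and partner to commit to contraception from at least 2 weeks before Day 1 until at least 6 months after the last dose. It adds, in parentheses, a "negative pregnancy test in women of childbearing potential". No other criterion in 7.1 and none in 7.2 mentions pregnancy. The nearest general exclusion is number 14 in 7.2, which begins "Any known pre-existing medical conditions that could interfere with" and goes on to the patient's participation in and completion of the trial.

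Section 10.3, under the side effects of ribavirin, calls teratogenicity a serious side effect and concludes that "it is recommended not to administer RBV to pregnant or breastfeeding women and to men whose partner is pregnant".

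Section 4.3 starts all patients on four weeks of peginterferon and ribavirin. It also says that the two drugs "will be administered in accordance with the approved technical data sheets"; those sheets are Annex I.

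The visit tables (sections 6.2 and 17) list "Inclusion and exclusion criteria" at selection and again on Day 1. They list "Confirmation of the use of contraceptive methods by the patient and his or her partner" at selection and at every treatment visit. The treatment table has a serum and a urine pregnancy test, both marked for women only.

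**The concern.** The protocol gives its own advice on who should not receive ribavirin, but puts it in the toxicity-management section. The list that a site works through to decide eligibility carries only part of that advice. A breastfeeding woman can have a negative pregnancy test and commit to contraception. A man whose partner is already pregnant can make the same commitment, because criterion 9 looks forward and does not ask about a current pregnancy. Either could meet the written criteria and then be due a drug that the protocol advises against in that situation.

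What is at stake is fetal and infant safety. There is also a practical side: a patient found unsuitable for ribavirin only after entry cannot start the regimen as planned, so selection is the better time to find out.

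**Working it through.** No power or sample-size arithmetic applies. The check sets the 10.3 note against the entry criteria and the visit tables.

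**Entry criteria.** 10 inclusion (7.1) + 16 exclusion (7.2) = 26.

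| Group in the 10.3 note | Criterion in section 7 that names it |
|---|---|
| Pregnant women | 7.1, criterion 9 (pregnancy test) |
| Breastfeeding women | none of 26 |
| Men whose partner is pregnant | none of 26 |

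So 1 of the 3 groups is covered.

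**Scheduled items.** The rows for the pregnancy tests are read from section 17, because the copy of the table in 6.2 may have been shifted when the text was extracted. Nothing here depends on the difference.

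| Table | Items | Reproductive items | Naming breastfeeding or a current partner pregnancy |
|---|---|---|---|
| Selection (6.2) | 14 | 1 (contraception confirmation) | 0 |
| Treatment (17) | 17 | 3 (contraception confirmation, serum test, urine test) | 0 |

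Of the three reproductive rows in the treatment table, the two tests are for women only, and no partner test is listed. The Day 1 recheck applies the same 26 criteria, so it gives a site a second chance to defer a patient but does not add the missing groups.

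**Planned ribavirin exposure (8.1), unless stopped early.**
- Week-4 fall reached and HCV RNA undetectable at week 8: 4 + 32 = 36 weeks.
- Week-4 fall reached but HCV RNA detectable at week 8: 4 + 32 + 12 = 48 weeks.
- Week-4 fall not reached, or cirrhosis: 4 + 44 = 48 weeks.

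These are planned durations for any patient. They are not an estimate of exposure in the two unnamed groups.

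**Consistency within the protocol.** Section 10.4 follows mother and newborn when the drug was taken by the woman's partner. The protocol therefore already treats exposure through a male patient as relevant, and asking about it before the first dose fits that approach.

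**The case against.** The best case against has four parts.

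1. *Criterion 9 may already cover partners.* Its subject is the patient and partner together, and the parenthesis on the pregnancy test is not expressly limited to patients. On that reading 2 of the 3 groups would be covered. The reading is strained: the scheduled tests are for women only and no partner test is planned. It would in any case leave breastfeeding uncovered.

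2. *Meeting the criteria is not the same as being dosed.* The data-sheet rule in 4.3 is mandatory, and the 10.3 note addresses exactly these groups. This stands in part. Either may stop dosing, but both govern how the drug is given, not who enters. How firmly the data sheets speak cannot be judged without Annex I. The consent sheet (Annex III) and the list of CRF variables (Annex VI) are also unseen and may prompt sites.

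3. *Other checks would bring such cases to light.* Confirming contraceptive use by both partners invites a conversation in which a current pregnancy would often emerge. Medical history is taken at selection, and exclusion 14 leaves some discretion. These help, but none asks the question. Exclusion 14 fits breastfeeding poorly, and a partner's pregnancy is not a medical condition of the patient. The rule in 6.6 and 7.3 that ends treatment for pregnancy during the study does not address breastfeeding or a partner already pregnant at entry.

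4. *A recommendation about a background drug need not be repeated as an entry criterion.* True, and 10.3 is worded as a recommendation. That limits the weight of the point; it does not make the two sections agree.

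**Conclusion.** The concern holds: the entry criteria in section 7 are not aligned with the ribavirin note in 10.3. As written, they admit two of the three groups for whom the protocol itself advises against the drug, and no scheduled item in the protocol body asks about either.

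The weight is minor. The number of patients affected cannot be derived from the documents and is probably small. Several indirect safeguards exist, and the unseen annexes may add more. Sample size, the SVR endpoint and its analysis are unaffected. The conclusion rests on reading the pregnancy test in criterion 9 as applying to patients, which agrees with the visit tables, and it is limited to the protocol body.

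**What to change.** Add one line to 7.2 (or extend criterion 9 in 7.1) excluding women who are breastfeeding and men whose partner is pregnant at entry. Ask about both at selection and on Day 1, within the contraception item already recorded at those visits.

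The cost is one line of protocol text and one question at two visits, with no new procedure or visit. The downside is that very few candidates would be deferred or not enrolled, and these are people whom 10.3 already advises against treating with ribavirin.
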